#### 5.3.2 Missing Data Imputation

Missing LDL-C data at week 12 will be imputed using the last post baseline observation carried forward (LOCF).

Observed data and LOCF data will be analyzed separately for primary and secondary efficacy endpoints.

#### 5.3.3 Sensitivity Analysis for Efficacy Endpoints

- A sensitivity analysis for primary and secondary efficacy endpoints will be performed using the ANCOVA model on Treatment Completer Analysis Set.
- The observed case data only (no imputations for missing data) analyses will also be used for sensitivity analyses for primary and secondary endpoints. Observed data analysis will be conducted using FAS.
- By-visit summary for all efficacy endpoints (LDL-C, non-HDL-C, HDL-C, TC, TG, ApoB, hs-CRP) will be provided for both conventional and standard units.

### **5.4 Exploratory Analyses**

For exploratory endpoints (change and percent change from baseline to Week 12 in HbA1C, fasting glucose,

HOMA-IR index, and 2-hour PPG), the data will be analyzed in the similar fashion as for the primary endpoints. For fasting plasma glucose,

HbA1C, 2-hour PPG and the baseline is the predose Day 1/Week 0 (Visit T1) value. If no value is available at Visit T1, then the last value prior to first dose of IMP will be used as baseline.

Sensitivity analyses will be used to examine if the potential data issues previously identified at 3 sites in Study (Sites ) impact the

Confidential

Page 20 of 38

Version 1.3, July 23, 2019 Statistical Analysis Plan

efficacy results of this study. The sensitivity analysis will repeat selected key analyses including all FAS subjects, as listed below:

- 1. Patient Disposition
- 2. Demographic and Baseline Characteristics Full Analysis Set
- 3. Summary Statistical Analysis of Percent Change from Baseline in Primary Efficacy Endpoints at Week 12 Full Analysis Set
- 4. Summary Statistical Analysis of Percent Change from Baseline in Secondary Efficacy Endpoints at Week 12 Full Analysis Set
- 5. Statistical Analysis of Median Percent Change from Baseline in hs-CRP and TG at Week 12 via Non-parametric Approach (Observed Data) Full Analysis Set
- 6. Statistical Analysis of Percent Change from Baseline in HbA1C Full Analysis Set
- 7. Statistical Analysis of Percent Change from Baseline in Fasting Glucose Full Analysis Set

8.			
9.			

Additional exploratory and sensitivity analyses may be performed as needed.

### 5.5 Safety Endpoints and Analyses

The safety and tolerability of FDC, EZE and PBO will be assessed by examination of TEAEs (including muscle related events and other AESI), physical exams, vital signs, electrocardiograms (ECGs), clinical laboratory values (serum chemistry, hematology, coagulation and urinalysis), and weight. All patients included in the Safety Analysis Set will be evaluated in the safety analyses.

Unless otherwise stated, descriptive summaries will be displayed by treatment group actually received and based on the Safety Analysis Set.

#### 5.5.1 Adverse Events (AEs)

AEs will be coded using the Medical Dictionary for Regulatory Activities (MedDRA) Version 21.0 or later and will be categorized by system organ class (SOC) and preferred term (PT). Patients with AEs that are ongoing at study completion or study withdrawal must be followed until resolution or for 30 days after the last study visit, whichever comes first. Summary tables will focus on TEAEs; however, listings will include all AEs (with non-TEAEs flagged).

Confidential

Page 21 of 38

In summary tables, TEAEs will be counted as "Not Related" if relationship to IMP was recorded as 'Not Related' or "Unlikely". Events will be counted as "Related" if relationship to IMP was recorded as 'Possible', 'Probable', 'Definite' or if relationship to IMP is missing.

The severity of the AE will be characterized as mild, moderate, or severe, to the following definitions:

- Mild: Events are usually transient and do not interfere with the subject's daily activities
- Moderate: Events introduce a low level of inconvenience or concern to the patient and may interfere with daily activities
- Severe: Events interrupt the subject's usual daily activity, are incapacitating with inability to do usual activities, or significantly affect clinical status and warrant intervention and/or close follow-up

Overviews of TEAEs will include total number of TEAEs and patient incidence of TEAE, TE SAE, related TEAE, related TE SAE, AESI, withdrew due to TEAE, Fatal TEAE. An individual TEAE summary will be presented by treatment group containing the following counts and percentages for:

- patients with TEAEs
- patients with TEAEs by PT
- patients with TEAEs by SOC, PT and maximum severity
- patients with treatment-related TEAEs
- patients with treatment related TEAEs by PT
- patients with treatment related TEAEs by SOC, PT and maximum severity
- patients with treatment-emergent serious adverse events (TE SAEs)
- patients with TE SAEs by PT
- patients with TE SAEs by SOC, PT and maximum severity
- patients with treatment-related TE SAEs
- Fatal AEs by SOC and PT
- withdrawal from IMP due to TEAEs

Patient incidence (percent of patients experiencing the AE) will be provided for overall TEAE, treatment related TEAE, TE SAE, treatment related TE SAE, and AESI.

The AE overview summaries will count a patient at most once in each AE category (at the "highest/most extreme" designation of each category regardless of preferred term) and percentages will be based on the total number of patients in the safety analysis set.

In addition to a comprehensive listing of all AEs (with non-TEAEs flagged), separate listings will be generated for SAEs, AEs resulting in withdrawal of IMP, and AEs with a fatal outcome.

Confidential

Page 22 of 38

#### 5.5.2 Adverse Events of Special Interest

Adverse events of special interest (AESI) will be identified based a pre-defined list of preferred terms provided by the sponsor (Appendix 2).

AESI will be presented in a listing and summarized by SOC, PT and treatment group.

In addition to adverse events, AESI is also being evaluated based on safety lab parameters.

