13.6.3.4. Monitoring and Management of Elevated Creatine Kinase Levels

If a subject has a value $>5 \times \text{ULN}$ for serum CK at any time after randomization, the subject will undergo a repeat confirmatory assessment as soon as is reasonably possible but preferably within 3 to 7 days after the laboratory result is available. This assessment will include questioning for related symptoms.

- If the repeat CK assessment confirms an unexplained (ie, not associated with recent trauma or physically strenuous activity) CK abnormality (value $>5 \times \text{ULN}$), the subject should, if asymptomatic, receive further assessment and investigation into the cause. The presence of renal injury should be assessed, and serum CK levels should be measured approximately weekly or more frequently, if clinically indicated, until resolution. If serum CK levels continue to rise, treatment with the IMP should be discontinued.
- If symptomatic, the following steps should be completed:
 - Hold dosing with the IMP;
 - Clarify the nature, duration, and intensity of muscle symptoms;
 - Review possible predisposing factors, such as unaccustomed exercise, heavy alcohol intake, viral illness (consider performing serology);
 - Evaluate for additional diagnoses or other conditions, which can cause myopathy, including muscle tenderness (by PE), weakness, rash, measurement of serum creatinine level, and dipstick urinalysis with microscopy, if indicated;
 - Obtain clinical chemistries to assess the possibility of lactic acidosis; and
 - Follow symptoms and serum CK levels until the abnormality has resolved.

If, based on the above evaluation, an alternative explanation is suspected, consider resuming IMP once the serum CK level returns to baseline levels. If no alternative explanation exists, consider withdrawing the subject from IMP treatment.

- If the repeat assessment confirms an unexplained (ie, not associated with recent trauma or physically strenuous activity) CK abnormality (serum CK value $>10 \times \text{ULN}$) even in the absence of symptoms, the subject should be withdrawn from the study and given no further doses of IMP. In all cases, signs/symptoms and laboratory evaluations, as outlined in the bulleted point above, should be evaluated.
- If the subject is withdrawn from IMP treatment, the subject should be asked to continue to be followed for safety (as outlined in the protocol-specified visit schedule in [Appendix 1](#)).

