13.6.3.5. Monitoring and Management of Potential Hypoglycemia and Metabolic Acidosis

Subjects will be educated on the signs and symptoms of hypoglycemia and will be instructed to report any signs and symptoms of hypoglycemia to the investigator.

Subjects will be reminded to report all signs and symptoms associated with hypoglycemia to the investigator at each study visit. For each occurrence of subject-reported signs and symptoms associated with hypoglycemia, the investigator will discuss these symptoms with the subject and assess whether they are attributable to hypoglycemia or to another potential cause. All investigator-confirmed occurrences of hypoglycemia will be recorded as AEs. All occurrences of signs and symptoms that are not confirmed by the investigator as attributable to hypoglycemia will be reported using the appropriate diagnosis.

Clinical laboratories will be assessed to determine any signs of anion gap metabolic acidosis. If laboratory test results are consistent with metabolic acidosis, the subject will be immediately contacted for further medical evaluation of the acidosis, and the event will be captured as an AE.

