13.7.1.3. Reporting of Adverse Events

All AEs that occur from the time the ICF is signed through 30 days after the last study visit should be recorded on the eCRF. Any SAE that occurs from the time the ICF is signed through 30 days after the last study visit should be reported to the sponsor per [Section 13.7.2.4](#).

Subjects should be instructed to report any AE that they experience from the time the ICF is signed through 30 days after the last dose of IMP to the investigator. Investigators should make an assessment for AEs at each visit and record the event on the appropriate eCRF.

Wherever possible, a specific disease or syndrome rather than individual associated signs and symptoms should be identified by the investigator and recorded on the eCRF. However, if an observed or reported sign or symptom is not considered a component of a specific disease or syndrome by the investigator, it should be recorded as a separate AE on the eCRF. Additionally, the condition that led to a medical or surgical procedure (eg, surgery, endoscopy, tooth extraction, transfusion) should be recorded as an AE, not the procedure.

Any medical condition already present at screening or baseline should not be reported as an AE unless the medical condition or signs or symptoms present at baseline change in severity or seriousness at any time during the study. In this case, it should be reported as an AE.

Clinically significant abnormal laboratory or other examination (eg, ECG) findings that are detected during the study or are present at baseline and significantly worsen during the study should be reported as AEs. The investigator will exercise his or her medical and scientific judgment in deciding whether an abnormal laboratory finding or other abnormal assessment is clinically significant. Significant abnormal laboratory values occurring during the clinical study will be followed until repeat tests return to normal, stabilize, or are no longer clinically significant. Any abnormal test that is determined to be an error does not require reporting as an AE.

Each AE is to be evaluated for duration, severity, seriousness, and causal relationship to the investigational drug. For each AE, the following information will be recorded:

- description of the event (eg, headache);
- date of onset;
- date of resolution (or that the event is continuing);
- action taken because of the event;
- seriousness of the event;
- severity of the event;
- outcome of the event; and

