#### Metabolic Acidosis

Metabolic acidosis events will be monitored by clinical safety laboratory chemistries. These events will be summarized by treatment group.

Confidential

Page 23 of 38

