#### Appendix 2: Adverse Event of Special Interest (AESI)

Adverse Event Terms per Protocol	Associated MedDRA Preferred Terms
Creatine kinase elevations	Blood creatine phosphokinase abnormal
Creatine kinase elevations	Blood creatine phosphokinase increased
Creatine kinase elevations	Blood creatine phosphokinase MM abnormal
Creatine kinase elevations	Blood creatine phosphokinase MM increased
New onset or worsening diabetes mellitus	Blood glucose abnormal
New onset or worsening diabetes mellitus	Blood glucose increased
New onset or worsening diabetes mellitus	Diabetes mellitus
New onset or worsening diabetes mellitus	Diabetes mellitus inadequate control
New onset or worsening diabetes mellitus	Diabetic ketoacidosis
New onset or worsening diabetes mellitus	Glucose tolerance impaired
New onset or worsening diabetes mellitus	Glucose urine present
New onset or worsening diabetes mellitus	Glycosuria
New onset or worsening diabetes mellitus	Glycosylated haemoglobin increased
New onset or worsening diabetes mellitus	Hyperglycaemia
New onset or worsening diabetes mellitus	Impaired fasting glucose
New onset or worsening diabetes mellitus	Ketoacidosis
New onset or worsening diabetes mellitus	Ketosuria
New onset or worsening diabetes mellitus	Ketosis

Page 35 of 38

Version 1.3, July 23, 2019 Statistical Analysis Plan

New onset or worsening diabetes mellitus	Type 2 diabetes mellitus
New onset or worsening diabetes mellitus	Urine ketone body present
Hepatic disorders	Alanine aminotransferase abnormal
Hepatic disorders	Alanine aminotransferase increased
Hepatic disorders	Aspartate aminotransferase abnormal
Hepatic disorders	Aspartate aminotransferase increased
Hepatic disorders	Blood bilirubin abnormal
Hepatic disorders	Blood bilirubin increased
Hepatic disorders	Hepatic enzyme abnormal
Hepatic disorders	Hepatic enzyme increased
Hepatic disorders	Hypertransaminaseaemia
Hepatic disorders	Liver function test abnormal
Hepatic disorders	Liver function test increased
Hepatic disorders	Transaminases abnormal
Hepatic disorders	Transaminases increased
Hypoglycemia	Blood glucose abnormal
Hypoglycemia	Blood glucose decreased
Hypoglycemia	Hypoglycaemia
Hypoglycemia	Hypoglycaemic coma
Hypoglycemia	Hypoglycaemic encephalopathy
Hypoglycemia	Hypoglycaemic seizure

Page 36 of 38

Version 1.3, July 23, 2019 Statistical Analysis Plan

Hypoglycemia	Shock hypoglycaemic
Metabolic acidosis	Metabolic acidosis
Muscular disorders	Muscular weakness
Muscular disorders	Muscle necrosis

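### The AESI preferred-term list has no clinical liver diagnoses and almost no non-keto acidosis terms, and the AESI laboratory flags have no acidosis criterion

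*SAP*

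**What the plan says.** SAP 5.5.2 gives two routes to an AESI. The first is by coded term: AESIs "will be identified based a pre-defined list of preferred terms provided by the sponsor (Appendix 2". They are then listed and summarized by SOC, preferred term and arm, and SAP 5.5.1 puts AESI incidence in the adverse event overview. The second is by laboratory value: "In addition to adverse events, AESI is also being evaluated based on safety lab parameters". SAP 5.5.3 lists the flags for this route, and 5.5.3.1 adds detail for the liver.

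The hepatic group in Appendix 2 consists of entries such as "Liver function test abnormal" and "Liver function test increased".

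On recording, Protocol 13.7.1.3 says: "Wherever possible, a specific disease or syndrome rather than individual associated signs and symptoms should be identified by the investigator and recorded on the eCRF". The same section asks that findings with a single cause be reported as one event. Under Protocol 13.6.3, the criteria for recording a laboratory value as its own adverse event apply only when the value is not already tied to one.

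On acidosis, Protocol 13.6.3.5 says: "Clinical laboratories will be assessed to determine any signs of anion gap metabolic acidosis". Results consistent with metabolic acidosis are to be followed up and captured as an adverse event. SAP 5.5.2 says "Metabolic acidosis events will be monitored by clinical safety laboratory chemistries" and adds that these events will be summarized by arm.

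**The concern.** A closed term list works only if it matches the way events are recorded. Here the recording rules steer a recognised liver illness towards a diagnosis, while the hepatic group accepts only laboratory terms. An isolated ALT rise recorded as an adverse event counts as a hepatic AESI; the same rise recorded as part of a diagnosed hepatitis does not.

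For acidosis, both documents promise laboratory monitoring, but the SAP gives no laboratory criterion to carry it out, and the term group has a single entry.

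At stake is the completeness of the AESI outputs, which readers use so that they need not search the full adverse event tables. An arm could show no AESI of these kinds while a relevant case sits in the general tables under another term.

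**Working it through.** The plan gives no figure to reproduce. The check is a count of Appendix 2, read against the recording rules and the laboratory flags.

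**1. Rows in SAP Appendix 2**

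| Group | Rows | Content relevant here |
|---|---|---|
| Creatine kinase | 4 | |
| New or worsening diabetes | 16 | includes diabetic ketoacidosis, ketoacidosis and ketosis |
| Hepatic | 13 | all laboratory findings |
| Hypoglycemia | 7 | |
| Metabolic acidosis | 1 | the term itself |
| Muscular | 14 | includes myopathy, rhabdomyolysis |
| Neurocognitive | 6 | |
| Renal | 17 | includes acute kidney injury, renal failure |

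Total: 4 + 16 + 13 + 7 + 1 + 14 + 6 + 17 = 78 rows.

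- The hepatic rows are ALT (2), AST (2), bilirubin (2), hepatic enzyme (2), hypertransaminasemia (1), liver function test (2) and transaminases (2): 2 + 2 + 2 + 2 + 1 + 2 + 2 = 13. Clinical diagnoses: 0 of 13.
- A search of all 78 rows for hepatitis, hepatic failure, jaundice, liver injury, cirrhosis and lactic returns nothing.
- Three rows name an acidosis: metabolic acidosis under its own heading, and ketoacidosis and diabetic ketoacidosis under diabetes.

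**2. Laboratory flags in SAP 5.5.3**

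There are 10 bullets: ALT/AST, total bilirubin, potential Hy's Law, CK, fasting glucose, HbA1C, creatinine, eGFR, hemoglobin decrease and low hemoglobin. Two are liver tests, a third combines them for Hy's Law, and none uses CO2 or anion gap. Protocol Table 3 already collects Na, Cl and CO2, from which anion gap = Na − (Cl + CO2).

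**3. Where example events would appear**

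| Event as recorded | AESI by term | AESI by laboratory flag | General AE tables |
|---|---|---|---|
| Isolated ALT increase | yes | if above 3 × ULN | yes |
| Hepatitis, with raised ALT as part of it | no | if sampled and above 3 × ULN | yes |
| Diabetic ketoacidosis | yes, under diabetes | no acidosis flag | yes |
| Metabolic acidosis | yes | no acidosis flag | yes |
| Lactic acidosis | no | no acidosis flag | yes |

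The hepatitis row depends on sampling. The scheduled on-treatment safety draws are at Day 28 and Day 85. An illness diagnosed between them reaches the laboratory outputs only if a study sample captures it. Lactic acidosis is a foreseeable entry because Protocol 13.6.3.4 includes this step for symptomatic confirmed CK elevation: "Obtain clinical chemistries to assess the possibility of lactic acidosis".

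**4. Size**

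One omitted subject at the SAP's 78 per arm: 1 / 78 = 1.3 percentage points of an arm's AESI incidence.

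**The case against.** The strongest reply is that the list is not the only route. SAP 5.5.2 also evaluates AESIs from laboratory data, with ALT/AST above 3 and 5 × ULN, bilirubin above 2 × ULN and a listing of potential Hy's Law cases. Protocol 13.6.3.1 requires a repeat liver assessment after a new ALT or AST above 3 × ULN. Protocol 14.8 itself defines the hepatic AESI summary through laboratory values, so a laboratory-based hepatic concept may be deliberate. Much of Protocol 13.7.3 is not shown, so the intended breadth cannot be judged. All this stands, and it limits the liver part. It does not explain why the liver group alone leaves out diagnoses that its renal and muscular counterparts include, nor does it restore the event to the AESI listing, table or overview count.

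On acidosis, the reply is that laboratory results consistent with it must be captured as an adverse event, and the protocol's own name for it is the listed term. That also stands, but no coded term is prescribed, and a more specific diagnosis falls outside the list. CO2 would presumably appear in the general out-of-range summary in SAP 5.5.3, but not as an AESI flag; that summary includes no anion-gap measure unless the gap is derived.

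Three stronger readings should be set aside:

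- **The most serious liver and acidosis events are missed.** A reader might infer this, but the laboratory outputs cover much of the liver, ketoacidosis is an AESI term under diabetes, and every event stays in the general TEAE, SAE or fatal tables as applicable.
- **Diagnoses are mandatory.** The recording rule is qualified: it says what should be done where possible.
- **The glucose term counts twice.** *Blood glucose abnormal* appears in two groups, but the specified table is by SOC and preferred term, where it is one row.

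**Conclusion.** The point holds as a minor gap and a cheap improvement. By coded term, the plan would omit clinical liver diagnoses and non-keto acidosis recorded under anything other than the single listed term. For acidosis, the promised laboratory monitoring has no AESI criterion in SAP 5.5.3.

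The effect is an incomplete AESI count, about 1.3 percentage points per omitted subject at 78 per arm. No event is lost from the study report, and the efficacy analyses are untouched. The documents give no expected rate for such events, so the number of cases affected is unknown and may be zero.

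The conclusion assumes that Appendix 2 is applied as written, with no further medical review or broader query, and that a diagnosis recorded by the investigator is coded to a diagnosis-level preferred term rather than to a laboratory term.

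**What to change.** Before unblinding:

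1. Add diagnosis-level terms to the hepatic group in SAP Appendix 2, or replace the group with a standard MedDRA query for drug-related hepatic disorders.
2. Add lactic acidosis and other acidosis terms to the metabolic acidosis group. State that ketoacidosis terms stay under diabetes, so that readers know where to find them.
3. Add to the AESI flags in SAP 5.5.3 a by-arm summary of low CO2 and of anion gap derived from Na, Cl and CO2, with thresholds chosen by the sponsor's safety team and written down in advance.

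The cost is an appendix edit, one derived laboratory variable and one or two extra table rows. No new samples or visits are needed. The downside is a slightly higher AESI count, which could arise in any arm.

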#### Hepatic Safety

For liver-associated enzymes and TB, the number and percent of subjects with abnormal values for ALT, AST and TB will be summarized. All liver-associated laboratory abnormalities will be assessed by Hy's Law criteria (>3 x ULN for either ALT or AST, with accompanying TB > 2 x ULN in the absence of other known causes) will also be applied to the data. Any potential Hy's Law cases will be listed separately.

#### Musculoskeletal Adverse Events

Muscle related adverse events as reported on the general AE CRF will be summarized by SOC and PT. In addition, the number and percent of subjects with abnormal CK values will be summarized. All muscle related events and details associated with it including cause and location will be provided in a listing.

